10.7.2 Minimal Residual Disease by NB5 Assay

We will use TLDA to determine the ability of each the three ^{131}I -MIBG regimens to reduce peripheral blood and bone marrow disease burden. Peripheral blood and bone marrow samples will be obtained at study entry and at the time of subsequent bone marrow evaluations. For each patient, we will calculate

their change in TLDA DG score from baseline to end of course 1 of therapy. The primary analysis will be an analysis of variance to compare this change in TLDA DG score in the bone marrow between randomized treatment groups. Secondary analyses will include evaluations of change in peripheral blood TLDA DG score as well as baseline level of blood and bone marrow disease burden by TLDA as predictors of response to ¹³¹I-MIBG therapy.

10.7.3 Evaluation of γ -H2AX Foci, Flt3 Ligand, Amylase, and DNA Damage Response Genes

For each radiation biomarker of interest, we will focus on comparing changes in each biomarker across the three randomized treatment arms. Each biomarker is a continuous variable, with values measured at 5 time points (two pre-¹³¹I-MIBG and one each at hours 72, 96, and Day 15 after start of ¹³¹I-MIBG infusion). We will determine the relative (percent) change of the post-¹³¹I-MIBG values from 2nd evaluation for each biomarker for each patient. The changes from the 1st to the 2nd value in the ¹³¹I-MIBG only arm will be used to estimate the within patient variability, while changes from the 1st to 2nd value in the other two arms will reflect the impact of each radiation sensitizer alone on each marker. Changes post ¹³¹I-MIBG will be presented in context with the estimated inpatient variation.

To determine the effect of radiation sensitizers on each biomarker, we will use an analysis of variance (comparing treatment arms) with repeated measures (change at 72 hours, at 96 hours, and at Day 15) to model the relative change of each biomarker as a function of randomized treatment arm and time. We will introduce a linear contrast to assess the general impact of the presence or absence of a radiation sensitizer (combining the irinotecan and vorinostat arms). Additional models will evaluate calculated whole body radiation exposure as a covariate in the model and separately as the outcome variable as a function of randomized treatment arm.

A series of secondary analyses will evaluate associations between baseline biomarker values and changes in biomarker values with toxicity and response to therapy. We will test for a univariate association between the baseline value or the degree of change in each biomarker and clinical response using two-sample t-tests, with patients separated into groups of responders (partial response or better after one course) and non-responders (less than partial response). We will evaluate an association with toxicity in a similar way, separating patients based on the presence or absence of grade ≥ 3 non-hematologic toxicity and also based on the presence or absence of grade ≥ 4 neutropenia or grade ≥ 4 thrombocytopenia in that course. Although testing will be two-sided, our expectation is that greater changes post ¹³¹I-MIBG in each of the biomarkers will be associated with higher response rates and greater toxicity. For each outcome, there will be 24 tests of association (6 biomarkers and 4 times). Nominal p-values will be reported without correction for multiple testing. Resampling will be used to assess robustness and internal validity of the univariate associations.

We will next construct a series of logistic regression models with response and toxicity (separately) as the dependent variables. Key covariates will include the relative change of the biomarker of interest, the baseline value, randomized treatment arm, the disease status (recurrent vs. primary refractory) and calculated whole body radiation exposure. If multiple biomarkers show promise, additional models will include covariates for each of these covariates or a composite biomarker score obtained using principal component analysis.

We will also evaluate whether patterns observed in the first course of therapy are seen during the second course of therapy, though the primary analyses will be based on data from the first course of therapy.

The sample size for the radiation biomarker studies is based on an estimated 80% participation rate, yielding 84 patients, or 28 patients per randomized arm. For the primary analyses, an analysis of variance with repeated measures will be used to establish an effect of either vorinostat or irinotecan on the amount of change in each biomarker. To obtain a (conservative) estimate of the power of the test of the effect of treatment arm, we will consider a one-way analysis of variance comparing the 3 arms at a single time point. With 28 patients in each arm, using a 0.05-level F-test for comparing the 3 mean changes, there will be 91% power when the true mean change in the group with the greatest change exceeds the true mean change in the group with the smallest change, by at least one “sigma” in magnitude – where “sigma” is equal to the common between-patient standard deviation (i.e. patient-to-patient variability).

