1.0 GOALS AND OBJECTIVES (SCIENTIFIC AIMS)

Primary Aim:

1.1

To identify the ^{131}I -MIBG treatment regimen associated with the highest overall response rate after one course of treatment on the following three arms: single-agent ^{131}I -MIBG; vincristine / irinotecan / ^{131}I -MIBG; or vorinostat / ^{131}I -MIBG

Secondary Aim:

1.2

To compare the toxicity profiles associated with each of the following three ^{131}I -MIBG treatment regimens: single-agent ^{131}I -MIBG; vincristine / irinotecan / ^{131}I -MIBG; or vorinostat / ^{131}I -MIBG

Exploratory Aims:

1.3

To describe best overall response for patients treated with two courses of therapy, site-specific response of bone marrow, soft tissue, and MIBG-avid lesions as well as overall survival and progression-free survival following each of three ^{131}I -MIBG treatment regimens

1.4

To assess peripheral blood and bone marrow minimal residual disease at study entry and following each of three ^{131}I -MIBG treatment regimens quantified using a neuroblastoma-specific NB 5-gene detection assay (NB5 assay) by TaqMan[®] low density array (TLDA)

1.5

To compare whole body radiation exposure in patients with neuroblastoma treated with each of three ^{131}I -MIBG treatment regimens

1.6

To evaluate peripheral blood lymphocyte γ -H2AX foci levels, expression of a panel of DNA damage response genes in peripheral blood mononuclear cells, plasma Flt-3 ligand, serum amylase, and circulating tumor DNA as markers of radiation exposure, response, and toxicity in patients with neuroblastoma treated with each of three ^{131}I -MIBG treatment regimens

1.7

To evaluate the performance of a computerized MIBG scan scoring system in patients with relapsed or refractory neuroblastoma treated with ^{131}I -MIBG therapy

1.8

To evaluate the association between tumor norepinephrine transporter (NET) protein expression and response to protocol therapy.

1.9

To describe the concordance rate between institutional Curie score and centrally reviewed Curie score in patients with relapsed or refractory neuroblastoma.

1.10

To describe the incidence and severity of sinusoidal obstruction syndrome (SOS) in patients with neuroblastoma who receive ^{131}I -MIBG therapy on this protocol and subsequently receive high-dose chemotherapy with stem cell rescue as part of their clinical care.

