8.0 CORRELATIVE BIOLOGY STUDIES

Collection of samples for correlative biology studies is optional and not required for study entry. Although these studies cannot be mandated, all institutions are strongly urged to submit specimens for all consenting patients.

Aside from submission of archival tissue to quantify NET expression (section 8.3), these studies are to be performed during both courses of therapy for patients enrolling prior to Amendment 7A and during the single allowed course of therapy for patients enrolling with Amendment 7A and later.

8.1 Evaluation of Minimal Residual Disease by 5 Gene NB5 assay TaqMan low density array (TLDA) Assay

All patients are required to co-enroll onto the NANT Biology Study, N04-05. Patients should submit blood and/or bone marrow at study entry and at the time of day 43-50 restaging studies. Submission of blood and bone marrow for NB5 TLDA assay will be according to the instructions in N04-05. Patients can submit only bone marrow for NB5 TLDA assay if blood volumes for research do not allow for blood submission.

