10.7 Analysis of Correlative and Exploratory Studies

The correlative biology studies are considered descriptive. Based on prior NANT studies, we anticipate that a minimum of 80% of patients will agree to participate in studies that require additional blood sampling.

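### Section 10.7.2 compares change in marrow DG score between arms without a baseline covariate; ANCOVA would be at least as precise, by an amount the documents do not fix

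*Combined protocol and SAP*

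**What the plan says.** Section 10.7.2 calculates for each patient "their change in TLDA DG score from baseline to end of course 1 of therapy". It then states: "The primary analysis will be an analysis of variance to compare this change in TLDA DG score" in bone marrow, by randomized arm. No covariate is named, neither the baseline DG score nor a stratification factor. The baseline score returns only in the secondary analyses, which take "baseline level of blood and bone marrow disease burden by TLDA as predictors of response to" therapy. That is a different question from the arm comparison.

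No other section fills the gap. The exact logistic regression in Section 10.3.2 adjusts for the stratification variables, but for clinical response. The models in Section 10.7.3 that contain a baseline value relate the radiation biomarkers to response and toxicity.

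Both measurements are already scheduled. Section 8.1 says: "Patients should submit blood and/or bone marrow at study entry and at the time of day 43-50 restaging studies". On status, the matching aim (1.4) is listed as exploratory, and Section 10.7 opens with: "The correlative biology studies are considered descriptive".

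**The concern.** Marrow burden at entry will probably vary widely. Section 3.2.5 asks only for MIBG uptake at one bone or soft-tissue site, and Section 10.2 stratifies on marrow involved or free of disease. Section 2.6.2 shows how often a marrow sample can have nothing to detect. Of 44 samples, 36 were negative by immunocytology and 20 of those were positive by TLDA, which leaves 36 − 20 = 16 negative on both. A patient with no detectable disease cannot improve further, while a heavily involved patient can. Change is therefore likely to depend on the starting value.

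If the true slope of follow-up on baseline is not 1, an analysis of raw change leaves the remaining dependence in the error term. It also carries any chance difference in baseline between arms into the estimated arm effect. At stake is the precision of the comparison of regimens on marrow disease burden, and nothing beyond that sub-study.

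**Working it through.** **Inputs.** The outcome, the method and the two time points come from Sections 10.7.2 and 8.1. The documents give no correlation (ρ) between baseline and follow-up DG score and no SDs. Both are assumed below and shown as ranges. The rank correlation of −.93 in Section 2.6.2 is between two assays on the same samples, so it cannot serve as ρ.

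**The plan's own figure.** No sample size or power is stated for NB5. The nearest figure is in Section 10.7.3, for the radiation biomarkers, and rests on an "estimated 80% participation rate, yielding 84 patients, or 28 patients per randomized arm" (0.80 × 105 = 84; 84/3 = 28). It gives 91% power for a 0.05-level F-test on three mean changes when the largest and smallest differ by one SD of the change. With means at −0.5, 0 and +0.5 SD, the noncentrality is 28 × (0.25 + 0 + 0.25) = 14. With 2 and 81 degrees of freedom the power is 0.918, so the figure reproduces. It is not a power statement for NB5.

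**Formulas.** Let l be the follow-up SD divided by the baseline SD. In units of the baseline variance, the per-patient variance behind each arm contrast is:

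- change score: 1 + l² − 2ρl
- ANCOVA: l²(1 − ρ²)

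The first minus the second equals (1 − ρl)². This is never negative, and it is zero only when the regression slope ρl is 1. With l = 1 the ratio of the two simplifies to 2(1 − ρ)/(1 − ρ²) = 2/(1 + ρ).

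**Variance of the change-score contrast relative to ANCOVA:**

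| l (assumed) | ρ = 0.3 | ρ = 0.5 | ρ = 0.7 |
|---|---|---|---|
| 1.0 | 2/1.3 = 1.54 | 2/1.5 = 1.33 | 2/1.7 = 1.18 |
| 1.5 | 2.35/2.0475 = 1.15 | 1.75/1.6875 = 1.04 | 1.15/1.1475 = 1.00 |
| 0.7 | 1.07/0.4459 = 2.40 | 0.79/0.3675 = 2.15 | 0.51/0.2499 = 2.04 |

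At l = 1.5 and ρ = 0.7 the slope is 1.05, which is why the gain almost vanishes. With equal SDs and ρ = 0.9 the ratio is 2/1.9 = 1.05.

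**Cost of the covariate.** At an illustrative 84 patients, estimating one slope inflates the ANCOVA variance by about 1 + 1/79 = 1.013. In the least favourable cell this turns the near-zero gain into a loss of about 1%.

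**Simulation.** With 4,000 trials per value of ρ, 28 per arm and equal SDs, the ANCOVA variance was 0.68, 0.74 and 0.88 of the change-score variance at ρ = 0.3, 0.5 and 0.7. The formula gives 0.65, 0.75 and 0.85, or 0.66, 0.76 and 0.86 with the inflation. The mean estimated effects agreed (1.003 and 1.001 at ρ = 0.5).

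**Imbalance.** If two arms differ by d in mean baseline score, the change-score contrast is shifted by (slope − 1) × d. When the relation is linear, ANCOVA removes that shift.

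**The case against.** The strongest reply is that this is a choice between two valid methods in a sub-study that the plan calls descriptive. The word primary in Section 10.7.2 means primary within an exploratory aim. No power or precision is promised for NB5, so no promise is broken. That stands and it limits the weight of the point. It does not remove it, because Section 10.7.2 specifies a comparison between arms, and a descriptive comparison also gains from narrower intervals.

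Three stronger readings might be inferred, and the documents do not support them:

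- **That the baseline score is wasted.** It enters every change score by subtraction and is used again as a predictor of response. What is given up is estimating its slope.
- **That the planned comparison is biased.** The arms are randomized, so the contrast is unbiased on average, as the simulation shows. A shift arises only given a chance imbalance in the trial as run. Section 10.2 partly limits this by balancing allocation on marrow involvement, though not on DG score among involved patients.
- **That the loss is 18% to 54%.** That is the equal-SD row alone (ratios 1.18 to 1.54), and equal SDs are doubtful if scores pile up at the detection limit.

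Two further objections hold. A linear ANCOVA does not by itself deal with scores at the limit. The number of paired marrow samples is also unknown: Section 3.1 only strongly encourages marrow submission, and Section 8.1 accepts blood or marrow. A gain in patients therefore cannot be stated.

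**Conclusion.** The point holds as a modest improvement. The direction is secure: with a linear relation and a common slope, ANCOVA is at least as precise as the planned change-score analysis apart from one degree of freedom, and it also removes the effect of chance baseline imbalance. The size is not secure. Over assumed correlations of 0.3 to 0.7 and SD ratios of 0.7 to 1.5, the variance of the planned contrast runs from about the same as that of ANCOVA to more than double it. Nothing in the documents narrows that range.

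A reader might infer that the trial's main conclusion is at risk. It is not. The NB5 result enters neither the primary response endpoint in Section 10.3.2, nor the selection rule in Section 10.1, nor the arm-dropping rule in Appendix VIII.

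**What to change.** In Section 10.7.2, replace the analysis of variance on change with an analysis of covariance. Compare the end-of-course-1 marrow DG score between arms, with baseline DG score and marrow involvement at entry as covariates, and do the same for the blood score. The sponsor can keep reporting change: with baseline as a covariate, modelling change or follow-up gives the same arm effect. A short statement on how scores at the detection limit are handled would sit well beside it.

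The cost is one sentence and two degrees of freedom, one per covariate. No new samples, visits or patients are needed, because both scores and the marrow stratum are already collected.

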Radiopurity is checked by both suppliers prior to shipment. Free radioiodine content is to be re-checked at the treating center prior to infusion according to the methods in Appendix IV and should be < 5% for ¹³¹I-MIBG from DraxImage and < 7% for ¹³¹I-MIBG from NDP.

The therapeutic dose of ¹³¹I-MIBG will be infused intravenously over 1.5-2 hours on day 1 of therapy with appropriate hydration, radiation isolation, thyroid blocking with potassium iodide and bladder protection with a Foley catheter.

The patient will remain in a radiation protected isolation room until radiation emissions meet institutional/state guidelines. This usually takes 3-5 days and then the patient can be discharged.

Patients should be transfused as needed to achieve a documented hemoglobin on the day of or one day prior to ¹³¹I-MIBG administration of ≥ 10 g/dL.

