4.3.2 Hydration

In order to ensure adequate hydration, patients will receive a minimum of 1.5-times maintenance rate IV fluids starting the night prior to ¹³¹I-MIBG infusion and continuing until radiation dose rate is < 7 mrem/hr at 1 meter. Once < 7 mrem/hr, IV hydration is at the discretion of the treating institution.

For patients assigned to the vorinostat / ¹³¹I-MIBG arm, the total IV plus oral fluid intake must be a minimum of maintenance rate until the patient has completed vorinostat therapy.

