4.3.4 Thyroid protection

Potassium iodide (KI) solution will be given in a loading dose of 6 mg/kg by mouth 8-12 hours prior to infusion of MIBG on Day 1, and then 1 mg/kg/dose by mouth starting 4-6 hours after completion of MIBG infusion and continuing every 4 hours on protocol Days 1 to 7 and then 1 mg/kg/dose by mouth once daily on protocol Days 8 to 43.

If ¹³¹I-MIBG infusion is delayed due to shipment or other issues and the patient has already received their loading dose, a suggested practice is to start the subsequent KI doses on schedule as though the ¹³¹I-MIBG infusion had been completed on schedule.

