8.2.2 Sampling scheduling

Samples will be obtained according to the following schedule. **Note that the schedule differs slightly based upon randomized arm of the study to which a specific patient has been assigned.**

Sample Timepoint (Obtain in Each Course)	Samples to be Obtained
Baseline Draw #1 
 For ¹³¹I-MIBG only arm: Anytime on the day prior to ¹³¹I-MIBG infusion (Protocol Day 0) For ¹³¹I-MIBG/vorinostat arm: Prior to first dose of vorinostat (Protocol Day -1) For ¹³¹I-MIBG/irinotecan/vincristine arm: Prior to first dose of vincristine/irinotecan (Protocol Day 0) 	2.5 mL in PAXgene RNA blood tube 5 mL in EDTA (usually purple top) 5 mL in serum separator (usually red top) tube
Baseline Draw # 2 Day of ¹³¹ I-MIBG infusion, anytime prior to start of infusion (all patients) = Protocol Day 1	2.5 mL in PAXgene RNA blood tube 5 mL in EDTA (usually purple top) 5 mL in serum separator (usually red top) tube
72 hours (+/- 2 hours) from start of ¹³¹ I-MIBG infusion (all patients) = Protocol Day 4	2.5 mL in PAXgene RNA blood tube 5 mL in EDTA (usually purple top) 5 mL in serum separator (usually red top) tube
96 hours (+/- 2 hours) from start of ¹³¹ I-MIBG infusion if patient still admitted to hospital (all patients) = Protocol Day 5	2.5 mL in PAXgene RNA blood tube 5 mL in EDTA (usually purple top) 5 mL in serum separator (usually red top) tube
Protocol Day 15 (or whenever patient receives stem cell infusion, if stem cell infusion does not occur on Day 15)	2.5 mL in PAXgene RNA blood tube 5 mL in EDTA (usually purple top) 5 mL in serum separator (usually red top) tube

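### Section 10.7.3 reads the pre-infusion biomarker change within Arms B and C as the sensitizer's own effect, without subtracting the same change in Arm A (minor)

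*Combined protocol and SAP*

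**What the plan says.** Section 8.2.2 schedules two draws before the infusion. Draw 2 is on Day 1, before the infusion starts, in every arm. Draw 1 is on Day 0 in Arms A and B, and on Day -1, before the first vorinostat dose, in Arm C.

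Section 10.7.3 gives the change between these draws two roles. The change in the ¹³¹I-MIBG "only arm will be used to estimate the within patient variability" (the first word of that quote belongs to the arm's name). In Arms B and C, "changes from the 1st to 2nd value in the other two arms will reflect the impact of each radiation sensitizer alone on each marker".

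The section opens with a general statement: "we will focus on comparing changes in each biomarker across the three randomized treatment arms". The model it then specifies is a repeated-measures analysis of variance across arms with three outcomes, "change at 72 hours, at 96 hours, and at Day 15", each measured relative to draw 2. The draw-1-to-draw-2 change is not an outcome in that model.

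Section 4.3, which applies to all arms, places several exposures at or near this interval:

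- Section 4.3.2: at least 1.5 times "maintenance rate IV fluids starting the night prior to" the infusion.
- Section 4.3.4: potassium iodide, which "will be given in a loading dose of 6 mg/kg by mouth 8-12 hours prior to infusion of MIBG on Day 1".
- Section 4.3.1: "Patients should be transfused as needed to achieve a documented hemoglobin on the day of or one day prior to" the infusion.

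**The concern.** Within Arm B or C, the draw-1-to-draw-2 change is the sum of the drug effect, whatever happened to all patients over the same period, and noise. The stated reading treats it as drug effect plus noise. Arm A supplies the noise term, but its mean change, which is what would measure the shared component, is not used.

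This is a before-and-after attribution inside a randomized trial that already has a control arm with two pre-infusion draws. A sensitizer could be credited with a shift that fluids, a transfusion or time of day produced, or a real rise could be masked by dilution. Because the post-infusion changes start from draw 2, this is also the only estimate in the plan of what each sensitizer does to the markers before radiation. Section 2.6.3 wants γ-H2AX to show whether either drug impairs DNA repair, so a clean drug-alone estimate is worth having.

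**Working it through.** **The plan's own figure.** Section 10.7.3 expects 80% participation: 0.80 × 105 = 84, or 28 per arm. It states 91% power for a 0.05-level F-test of three mean changes when the largest and smallest differ by one SD. With means -0.5, 0 and +0.5 SD, the noncentrality is 28 × (0.25 + 0 + 0.25) = 14 on 2 and 81 degrees of freedom, which gives 91.8%. The figure reproduces. It concerns the between-arm comparison, which the present point does not touch.

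**What each reading estimates.** Let s be the mean change shared by all arms, e the sensitizer effect and σ the SD of the draw-1-to-draw-2 change.

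- Within Arm B: expected change = e + s, standard error σ/√28 = 0.189σ.
- B minus A: expected difference = (e + s) - s = e, standard error σ√(2/28) = 0.267σ.
- Ratio of standard errors: √2 ≈ 1.41.

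**Illustration with no drug effect (e = 0).** The documents give no value for s, so a range is assumed. The plan names no test for this interval; a two-sided 0.05 t-test stands in for reading the mean change as real. The within-arm figures use the noncentral t distribution with 27 degrees of freedom and noncentrality (s/σ)√28. Simulation of 20,000 trials at shifts of 0, 0.25 and 0.5 SD agreed, and there the B-versus-A test gave 4.9%, 5.0% and 5.4%.

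| Assumed shared shift (SD) | Apparent effect, within arm | Apparent effect, B versus A |
|---|---|---|
| 0 | 5% | 5% |
| 0.1 | 8% | 5% |
| 0.2 | 18% | 5% |
| 0.3 | 33% | 5% |
| 0.5 | 72% | 5% |

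**Illustration of masking.** Take e = +0.5 SD and s = -0.3 SD. The within-arm mean is +0.2 SD, detected about 18% of the time. The contrast with Arm A still estimates +0.5 SD (noncentrality 0.5 × √14 = 1.87) and detects it 45% of the time.

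**Arm C.** From draw 1 to draw 2 is Day -1 to Day 1 in Arm C, against Day 0 to Day 1 in Arm A: about 48 hours against about 24. If a shared change accumulated with time at an assumed 0.25 to 0.5 SD per 24 hours, C minus A would retain that extra amount and show an apparent effect in 15% to 45% of cases. The contrast isolates the drug for B on a day-matched basis, but not fully for C.

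**The case against.** The best defence is that the plan never rules out a comparison with Arm A. It opens by promising comparisons of changes across the three arms and describes this interval for all three arms in one sentence. A reader might infer that the plan has decided against any contrast. The documents do not support that; they simply do not state one. The general opening is not tied to this interval, though, and the specific sentence gives Arm A a variability role and Arms B and C an effect role, so the gap stands.

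A reader might also infer that the post-infusion findings are contaminated. They are not. Those changes are compared between randomized arms, and 10.7.3 says they will be presented against the estimated within-patient variation, which comes from Arm A, and not against the pre-infusion change in B and C.

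Three further points stand and limit the concern:

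- Section 10.7 calls these studies descriptive and no test of this interval is planned, so the rates above are not operating characteristics of the plan.
- A shared shift is plausible but not shown. Transfusion is only as needed and may precede draw 1. Dilution bears most directly on plasma Flt3 ligand and serum amylase; no such route is evident for γ-H2AX in fixed cells or for gene expression.
- The contrast with Arm A is imperfect for Arm C.

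**Conclusion.** The point holds in a narrow form. As written, 10.7.3 attributes the whole draw-1-to-draw-2 change in Arms B and C to the sensitizer, and no stated analysis removes a change common to all arms. A better estimate is available from samples already scheduled.

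The size of the bias equals the size of the shared shift, which the documents do not give. If that shift is zero, nothing is lost. The figures of about 18% at 0.2 SD and 72% at 0.5 SD assume 28 patients per arm, normal changes with equal SD, no drug effect and a within-arm test at 0.05.

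The consequence is limited to one descriptive estimate under exploratory Aim 1.6, on optional samples. The 91% power, the primary endpoint, arm selection and safety monitoring are unaffected. Priority: minor.

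**What to change.** In 10.7.3, replace the sentence on the first-to-second change with wording such as: the effect of each sensitizer before ¹³¹I-MIBG will be estimated as the draw-1-to-draw-2 change in that arm minus the draw-1-to-draw-2 change in the ¹³¹I-MIBG-only arm (B minus A, C minus A), with 95% confidence intervals; the spread of the change in the ¹³¹I-MIBG-only arm will continue to serve as the within-patient variability.

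Add one limitation: B minus A is matched by day, but Arm C's interval starts on Day -1 against Day 0 in Arm A, so C minus A does not fully separate vorinostat from time.

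The cost is a wording change and no new samples. The price in precision is a standard error about 1.4 times the within-arm one. With 28 per arm, the 95% half-width goes from about 2.05 × 0.189 = 0.39 SD to about 2.00 × 0.267 = 0.53 SD.
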